- The protocol team should be notified of a Grade 4 event at [contact].

NOTE: Topical corticosteroids, topical anti-pruritic agents, and oral H1-antihistamines (such as cetirizine, diphenhydramine, hydroxyzine and levocetirizine but excluding astemizole and terfenadine) will be allowed at the investigator's discretion for all grades of rashes.

6.14 Management of Acute Systemic Allergic Reaction

The table in Appendix VII-B illustrates these grading and management guidelines. Grade 1

Localized urticaria with no medical intervention indicated. Subject may continue intake of ETR.

Grade 2

Localized urticaria with medical intervention needed, or mild angioedema with no medical intervention indicated. Subject may continue intake of ETR.

Grade 3

Generalized urticaria or angioedema with medical intervention indicated; or symptomatic mild bronchospasm.

- Subjects with Grade 3 acute systemic allergic reactions will be permanently discontinued from the investigational medication (ETR) and background regimen but will be followed on study on a modified schedule (Appendix ID) for safety outcomes.
- Subjects will be treated as clinically appropriate per the local physician.

Grade 4

Acute anaphylaxis; life-threatening bronchospasm; laryngeal edema.

- Subjects with Grade 4 acute systemic allergic reactions will be permanently discontinued from the investigational medication (ETR) AND background regimen (OBR) but will be followed on study on a modified schedule (Appendix ID) for safety outcomes.
- Subjects will be treated as clinically appropriate per the local physician.
- The protocol team should be notified of a Grade 4 event at [contact].

6.15 Management of Abnormal QTc or PR intervals noted onECG

NOTE: Please refer to Appendix V for grading of abnormal QTc or PR intervals by ECG. Any subject who is permanently discontinued from the investigational medication (ETR) because of toxicity will be followed on study on a modified schedule (Appendix IE) for safety outcomes. Subjects will be treated as clinically appropriate per the local physician.

Grade 1

Continue study drug; routine monitoring. Grade 2

Continue study drug; work-up to exclude other causes according to judgment of site investigator. Grade 3

- Study drugs may be continued at the discretion of the site investigator/clinician.
- Based on the local investigator reading of the ECG, sites should request a turnaround time of 24 hours for the ECG from the centralized reading service.
- If the central ECG reader confirms a Grade 3 ECG abnormality (QTc and/or PR interval), ETR must be permanently discontinued.
- For Grade 3ECG abnormalities that are determined to be unrelated to study drug, the investigator should contact the team to determine whether study drug may be safely resumed.

Grade 4: Non-Life-Threatening Toxicity

- Subjects experiencing a Grade 4toxicity must have ETR discontinued.
- OBR should be held at the discretion of the site investigator.
- Based on the local investigator reading of the ECG, sites should request a turnaround time of 24 hours for the ECG from the centralized reading service.

- The protocol team should be notified of a Grade 4 event at [contact].
- If the central ECG assessment confirms Grade 4 ECG abnormalities (QTc and/or PR interval), ETR must be permanently discontinued. OBR should be held at the discretion of the site investigator.
- For Grade 4ECG abnormalities that are determined to be unrelated to study drug, the investigator should contact the team to determine whether study drug may be safely resumed.
- If subjects are discontinued from ETR, they will still be followed on study on a modified schedule (Appendix ID) for safety outcomes. Subjects will be treated as clinically appropriate per the local physician.

Grade 4: Life-Threatening Toxicity

- Subjects experiencing a life-threatening Grade 4toxicity must have ETR discontinued
- OBR should be held at the discretion of the site investigator.
- Sites should request a turnaround time of 24 hours for the ECG from the centralized reading service.
- The protocol team should be notified of a Grade 4 event at [contact].
- For confirmed drug-related, life-threatening Grade 4 QTc or PR interval SAEs, study medication must be permanently discontinued.
- For life-threatening Grade 4 ECG abnormalities that are determined to be unrelated to study drug, the investigator should contact the team to determine whether study drug may be safely resumed.
- If subjects are discontinued from ETR, they will still be followed on study on a modified schedule (Appendix ID) for safety outcomes. Subjects will be treated as clinically appropriate per the local physician.

6.16 Management of Neurologic Adverse Events

NOTE: Please refer to Appendix VI for grading abnormal neurologic adverse events. Grade 1

Continue study drug; routine monitoring.

Grade 2

Continue study drug; work-up to exclude other causes according to judgment of site investigator. Grade 3

- Subjects experiencing a Grade 3toxicity must have ETR discontinued
- OBR may be discontinued at the discretion of the site investigator.
- The protocol team should be notified of a Grade 3 event at [contact].
- For Grade 3 adverse events that are determined to be unrelated to study drug, the investigator should contact the team to determine if/when the study drug may be safely resumed
- If the event is considered to be ‘definitely related,’ ‘probably related’ or ‘possibly related’
- to study drug, AND is resolved to grade 2 or less, AND the site physician feels it is in the subjects best interest to re-try the drug, the investigator should contact the team to determine if/when the study drug may be safely resumed
- If subjects are permanently discontinued from ETR, they will still be followed on study on a modified schedule (Appendix IE) for safety outcomes. Subjects will be treated as clinically appropriate per the local physician.

Grade 4: Non-Life-Threatening Toxicity

- Subjects experiencing a Grade 4 adverse event must have ETR discontinued temporarily
- OBR should be held at the discretion of the site investigator.
- The protocol team should be notified of a Grade 4 event at [contact].
- For Grade 4 adverse events that are determined to be unrelated to study drug, the investigator should contact the team to determine when/if study drug may be safely resumed.
- If the event is considered to be definitely related, probably related or possibly related to study drug, ETR should be permanently discontinued.
- If subjects are discontinued from ETR, they will still be followed on study on a modified schedule (Appendix ID) for safety outcomes. Subjects will be treated as clinically appropriate per the local physician.

Grade 4: Life-Threatening Toxicity

- Subjects experiencing a Grade 4 toxicity must have ETR discontinued permanently; but should remain on study for safety follow-up.
- OBR should be held at the discretion of the site investigator.
- The protocol team should be notified of a Grade 4 event at [contact].
- If subjects are discontinued from ETR, they will still be followed on study on a modified schedule (Appendix ID) for safety outcomes. Subjects will be treated as clinically appropriate per the local physician.

6.2 Subject Management

The DMC will maintain a web page informing sites as to the availability of enrollment slots per cohort. The protocol team, including the co-chairs, medical officers, pharmacist, and pharmacologist, will respond to sites who contact the team with questions regarding toxicity management, dose modifications, or other issues within 1 business day. Team responses will include, at a minimum, the study team.

Sites will be given 7 days to respond to queries to allow the team to meet Janssen R&D data delivery requirements. Sites will be contacted by the protocol data manager or co-chairs regarding any query responses or data issues that are outstanding after 7 days. All dose modifications will be recommended by the protocol team. See Section 3.0 for detailed information on the review process and dose modifications for a mini-cohort or full cohort.

Information on permitted ARV changes can be found in Section 6.5.

6.3 Definition of Virologic Failure for Subject Management

NOTE: A confirmatory (repeat) HIV-1 RNA measurement MUST be performed within 1 to 4 weeks of the initial suspected failure or rebound.

Virologic FAILURE or lack of response in this study is defined as:

- A confirmed HIV-1 RNA at week 8 that is not at least 0.5 log lower than the HIV-1 RNA at entry (unless the viral load at week 8 or later is already \leq 400 copies/mL)
OR
- A confirmed HIV-1 RNA at or after week 12 that is not at least 1 log lower than the HIV RNA at entry (unless the viral load at week 12 or later is already \leq 400 copies/mL)
OR
- A confirmed HIV-1 RNA \geq 400 copies/mL at week 24

Virologic REBOUND in this study is defined as:

For subjects whose nadir was \leq 400 copies/mL; a confirmed HIV-1 RNA $>$ 1000 copies/mL (on 2 consecutive measurements at least 1 week but no more than 4 weeks apart).

Subjects, who are confirmed as virologic failures (including virologic rebound) as defined above, should follow the schedule of evaluations for Virologic Failure as described in Appendix IA – IC. At the confirmed virologic failure visit, a specimen should be drawn that should be sent for resistance testing (genotyping and phenotyping), as described in Appendix IA – ID.

Subjects will then, at the discretion of the subject's clinician; with the approval of the protocol team and assuming the subject agrees to continue; be moved into one of the following three options:

- Off Study Drug – On Study: Be taken off study drug and followed as per Appendix ID, 'Follow up for Subjects who Discontinue Study Provided Etravirine;'

OR

- On Study Drug – re-optimize OBR: Have background therapy re-optimized, with the subject remaining on study drug;

OR

- On Study Drug: Continue with no changes made to the current regimen.

Any re-optimization of background therapy that includes experimental drugs must first be approved by the P1090 core team by emailing a request to [contact].

6.4 Viral Resistance Testing

For all subjects, blood samples for viral resistance assays will be collected at screening. In addition, to evaluate development of resistance to ETR and to other antiretroviral therapies, used in the treatment regimen, blood samples will be collected at any confirmed virologic failure (including virologic rebound) and at any early discontinuation visit (if not already obtained at virologic failure) to assess development of resistance to ETR and or OBT. (Refer to Appendix I for more information)

6.5 Permitted Changes to the ARV Optimized Background Therapy During the Study

Any changes in background ARV therapy after initial optimization must be approved by the P1090 core protocol team. Unless the change is specifically permitted, subjects who have one or more new agents added to the optimized background CART regimen will be considered virologic failures.

The following changes to optimized background therapy are permitted during the study. However, the P1090 core protocol team requests that they be notified of any of these changes BEFORE they occur ([contact]).

- Subjects may discontinue a background ARV (if approved by the P1090 team) and remain on study and on study drug
- Formulation substitutions for NRTI class (substituting single agents for fixed dose combinations and vice versa of the same ARV, or switching from liquid to pill/capsule form) are allowed.
- Formulation substitutions for PI class (capsule to tablet or liquid, or vice versa) are permitted only after discussion with the P1090 core protocol team, including the pharmacologists. In certain cases, repeat PK evaluations may be requested
- Substitution within the NRTI or PI class, for reasons of toxicity or intolerance will be considered. If approved, the subject will remain on study drug, with the new PI, but considered as a virologic failure if the change occurs after the week 4 visit.

6.6 Concerns Regarding Non-Adherence

In the rare event where the results of a single subject's intensive PK are extremely low, AND the site clinician/protocol team strongly suspect non-adherence, an additional subject may be enrolled into the mini-cohort to replace the non-adherent subject. The non-adherent subject may remain on study and on study drug (ETR) but will not be considered for dose-finding or safety final analysis.

Medication adherence is critical to successful antiretroviral therapy. In addition to compromising the efficacy of the current regimen, suboptimal adherence has implications for limiting future effective regimens for subjects with resistant strains.

Evidence indicates that adherence problems occur frequently in children. Studies have reported that fewer than 50% of children and/or their caretakers reported full adherence to the regimens. Although a variety of factors have been associated with adherence, no clear predictors of either good or poor adherence have been consistently identified in children.

As a part of this trial, adherence to therapy should be stressed at each visit, along with continued exploration of strategies to maintain and/or improve adherence.

Multiple methods of determining adherence to ARV therapy will be used simultaneously (e.g., quantitative self-report, pill counts). Pill counts will take place at each visit and will be recorded on the drug accountability form. Adherence to the study drug, OBR, and assessment of the palatability of the study drug, will also be monitored in the form of questionnaires/CRF administered by the site staff.

6.7 Etravirine Dose Changes Due to Increases in Body Weight

Confirmed increases in subject's body weight will trigger an ETR dose increase as follows:

- If NO PK directed dose change was made following the day 14 (\pm 4 days) PK visit, i.e., the starting ETR dose from dosing tables provided an adequate AUC_{12h} , then as the subject's weight increases such that it crosses into a higher weight band, the dose will be changed to correspond with the new weight band, consistent with the Dosing Table provided in Appendix III.
- If an individualized PK directed dose change was made following the day 14 (\pm 4 days) PK visit, a dose increase is triggered when the subject's weight has increased by 25% from the weight at the most recent AUC_{12h} evaluation. Contact the protocol team at [contact] for an individualized dosing recommendation based on the subject's pharmacokinetic parameters.

There will be no 12-hour pharmacokinetic studies for dose adjustments due to increase in body weight.

6.8 Criteria for Etravirine (Study Drug) Discontinuation

The following are criteria that will result in discontinuation of study treatment (ETR). Subjects who are withdrawn from study drug within the first 48 weeks of study will not enter long term follow-up, but will be followed for safety for 4 weeks, as per Appendix ID.

Additionally, any AEs will be followed until satisfactory clinical resolution (i.e. value returns back to subjects baseline value) or stabilization (to be agreed upon with the sponsor). All Grade 3 and Grade 4 laboratory abnormalities as well as any laboratory abnormalities resulting in an increase of 2 DAIDS grades from baseline will be followed until they return to baseline or within 1 grade from baseline.

- Grade 3 or higher events that are believed to be related, or possibly related, to study drug
- Treatment with disallowed medications
- Grade 3 or higher cutaneous reactions as outlined in section 6.13, that are not clearly related to a specific viral illness
- Grade 3 or higher acute systemic allergic reactions as outlined in section 6.14, that are related to study drug
- Other Grade 3 or higher toxicities that don't resolve to < Grade 3
- Grade 3 or higher ECG toxicities (QTc and/or PR interval) as outlined in Section 6.15, that are deemed related to study drug
- Grade 3 or higher neurologic adverse events as outlined in Section 6.16
- For subjects who have an $AUC > 4380\text{ng.h/mL}$, but who cannot be dose reduced
- Non-adherence to study medication or study medication administration instructions
- New data become available that indicate treatment should be discontinued
- Subject declines further study visits, including PK visits

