9.34 Individual Subject Dose Evaluation and Adjustments

Doses of ETR will be adjusted in an individual subject to attain an AUC_{12h} of $< 2350 \text{ ng}\cdot\text{h}/\text{mL}$.

- If the subject's current dose is well tolerated (no toxicity \geq Grade 3) but AUC_{12h} is $< 2350 \text{ ng}\cdot\text{h}/\text{mL}$, then a new dose will be determined by prorating the current dose to attain an AUC_{12h} of approximately $2864 \text{ ng}\cdot\text{h}/\text{mL}$ (the 20th percentile of exposure in adults). The maximum dose increase for the initial PK-guided dose adjustment would be capped at the adult dose of 200 mg twice daily. If a second PK evaluation again reveals an $AUC_{12h} < 2350 \text{ ng}\cdot\text{h}/\text{mL}$, then the dose may be increased above the 200 mg twice daily initial BID cap, again, targeting an AUC_{12h} of approximately $2864 \text{ ng}\cdot\text{h}/\text{mL}$.
- If the subject's AUC_{12h} is $> 4380 \text{ ng}\cdot\text{h}/\text{mL}$ (the median AUC_{12h} value in adults receiving ETR 200 mg twice daily) but current dose is not well tolerated (no toxicity \geq Grade 3) then the dose will be prorated, if possible given available dosage forms to achieve an AUC_{12h} of $4380 \text{ ng}\cdot\text{h}/\text{mL}$. If no dose reduction is possible, then the subject will be discontinued from study treatment.
- If a subject has not achieved an AUC_{12h} of $< 2350 \text{ ng}\cdot\text{h}/\text{mL}$, but is experiencing a Grade 3 or greater toxicity that is deemed probably or definitely related to study drug, that subject will be discontinued from study treatment.

Although ETR displays non-proportional PK, dose adjustments will be prorated on a linear scale using multiples of 12.5 mg (the smallest incremental dose change possible given the available formulations).

Initial PK-guided dose increases will be capped at the adult dose of 200 mg twice daily. However, if after a second PK evaluation the subject's AUC_{12h} has not achieved the minimum target (2350 ng•h/mL), doses may exceed 200 mg twice daily. The core protocol team will communicate all individual dose adjustments to the participating site.

All subjects with an individual dose adjustment (not related to weight gain) will have repeat intensive 12 hour PK evaluations performed between Day 7 to 14 after initiation of the new dose.

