As detailed in Section 3.0 of the protocol, subjects may be dose-adjusted to the new dose and additional new subjects will be treated at the new dose, and safety and PK will be evaluated as described.

If more than 2 of the 6 children in a cohort has an AUC_{12h} greater than the 75th percentile of adult values (6339 ng•h/mL) and the cohort has passed the safety criteria, the team will review the starting dose and the expected distribution of ETR C_{12h} and AUC_{12h} . This review is to assess the goal of objective of achieving a distribution for ETR C_{12h} and AUC_{12h} values in children that approximates that in HIV-1-infected treatment experienced adults. The team may decide to revise the starting dose; however, there is no requirement for the team to adjust the starting ETR dose.

If the starting dose for a cohort of older subjects is revised, the protocol team may preemptively change the starting dose for subsequent younger cohort that has not yet opened to enrollment. Any change in the starting dose will be communicated by the protocol team to all participating sites, with instructions to use the appropriate table of starting doses. It is not unreasonable to suspect that the three cohorts planned for enrollment may each have different dosage requirements. This protocol will determine appropriate doses for each of these strata.

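### The AUC12h >4380 rule is wrong as written: Section 9.34 reverses its definition of a poorly tolerated dose, and Section 6.8 repeats the stopping rule with no tolerability condition

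*Protocol*

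**What the plan says.** Protocol Section 6.8 opens its list with "The following are criteria that will result in discontinuation of study treatment (ETR", so the list is mandatory. One entry is an AUC above 4380 ng·h/mL in subjects "but who cannot be dose reduced". It names no toxicity and does not point to Section 9.34, although the rash, allergy, ECG and neurologic entries each cite their own section. Toxicity has a separate first entry: "Grade 3 or higher events that are believed to be related, or possibly related, to study drug".

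Protocol Section 9.34 governs individual dose adjustment.

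- Its first bullet, on low exposure, applies when the "current dose is well tolerated (no toxicity" of Grade 3 or above). Here the parenthesis explains good tolerability.
- Its second bullet, on AUC12h above 4380, applies when exposure is high "but current dose is not well tolerated (no toxicity" of Grade 3 or above). The same parenthesis now explains poor tolerability. For such a child, "then the dose will be prorated, if possible given available dosage forms to achieve an" AUC12h of 4380. The bullet ends: "If no dose reduction is possible, then the subject will be discontinued from study treatment".

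Sections 9.34 and 9.35 identify 4380 as the adult median. Section 9.35 also says that if more than 2 of 6 children exceed the adult 75th percentile (6339) and the cohort has passed safety, the team reviews the dose, but "there is no requirement for the team to adjust the starting ETR dose".

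The SAP leaves pharmacokinetics to the protocol pharmacologist (Section 6.3) and does not restate or correct either rule.

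**The concern.** The same threshold and the same consequence appear twice under different conditions. In 9.34 the condition is poor tolerability, but its definition is reversed. In 6.8 the condition is missing. A site that reads only 6.8 finds a stopping rule based on exposure alone. A site that follows the cross-references to 9.34 elsewhere in the protocol finds a parenthesis describing a child without severe toxicity, so 9.34 read literally does not repair 6.8.

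The child at risk is one who tolerates ETR at ordinary adult exposure. Section 1.31 reports that AUC12h did not correlate with adverse events in adults, so the documents give no safety reason to act on an AUC just above the median. Section 1.4 describes children with few or no other treatment options. A child stopped before week 48 goes to the 4-week safety follow-up and does not enter long-term follow-up. A child reduced on AUC alone would no longer have been treated exclusively at the cohort's optimal dose, which Section 8.1 requires for evaluability.

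**Working it through.** **Inputs.** Cohort target 2713 to 6783, set at 60% to 150% of the adult geometric mean (9.31, 9.351). Earlier window 3618 to 5879, set at 80% to 130% (1.32). Adult median 4380 and 75th percentile 6339 (9.351). Adult 10th percentile 2350 (9.31). DUET mean 5506, SD 4710 (1.32, Tables 2 and 3). Dose step 12.5 mg (9.34). Lowest dose considered 12.5 mg and lowest tabled dose 25 mg (Appendix III).

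**1. Reproduce the plan's target.** The adult geometric mean follows from each limit: 2713/0.60 = 4521.7; 6783/1.50 = 4522.0; 3618/0.80 = 4522.5; 5879/1.30 = 4522.3. All give about 4522. In reverse, 0.60 × 4522 = 2713 and 1.50 × 4522 = 6783. The stated target reproduces.

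**2. Place the threshold against it.** 4380/4522 = 0.97, so 4380 lies just below the adult geometric mean that the dosing tries to match. The upper accepted cohort mean is 6783/4380 = 1.55 times the threshold. The level that prompts only a review in 9.35 is 6339/4380 = 1.45 times it.

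**3. Share of children above 4380.** Assumption: log-normal AUC12h with the adult spread, since the documents give no spread for this age group. Three estimates of the log-SD:

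- ln(4522/2350)/1.2816 = 0.511
- ln(6339/4380)/0.6745 = 0.548
- √ln(1 + (4710/5506)²) = 0.741

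P(AUC > 4380) = 1 − Φ(ln(4380/GM)/SD):

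| Cohort geometric mean | SD 0.511 | SD 0.548 | SD 0.741 |
|---|---|---|---|
| 2713 | 17.4% | 19.1% | 25.9% |
| 4522 | 52.5% | 52.3% | 51.7% |
| 6783 | 80.4% | 78.8% | 72.2% |

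The AUC half of the rule is therefore met often at a successful dose. These are not children stopped, because 6.8 also requires that the dose cannot be reduced.

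**4. Who cannot be dose reduced?** Neither section defines this.

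- *Any lower step counts.* The lowest tabled dose gives 25 − 12.5 = 12.5 mg, which is available. Nobody is stopped.
- *The dose prorated to 4380 is rounded to the nearest step* (an assumption; 9.34 asks only for multiples of 12.5 mg). The dose d returns to itself when AUC < 4380·d/(d − 6.25). On 25 mg the limit is 5840, and 15.2% to 21.7% of children fall between 4380 and 5840 at geometric mean 4522. On 100 mg the limit is 4672, with 3.5% to 5.0%. If the prorated dose is rounded down instead, a reduction always exists and nobody is stopped.
- *The lower dose must also keep AUC12h at 2350 or above* (a floor that neither the 6.8 bullet nor the reduction bullet states), assuming proportional exposure. On 25 mg, halving the dose goes below 2350 when AUC < 2 × 2350 = 4700, and 3.8% to 5.5% of children fall between 4380 and 4700 at geometric mean 4522.

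The documents do not choose among these readings and do not give the number of children at each dose, so no total follows.

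**The case against.** The strongest reply is that 6.8 is harmless in practice. Every tabled dose can be lowered by 12.5 mg, so read at its plainest the bullet stops no one. A child who cannot be reduced is presumably one for whom a reduction was called for, and the only individual reduction rule at 4380 is in 9.34, which is about poorly tolerated doses. Sites do not act alone: Section 6.2 has the protocol team recommend all dose modifications, and 9.34 has the core team communicate them. All of this stands, and it keeps the point minor. It does not make the text right. A mandatory stopping criterion should not depend on inferring a missing condition from a section that defines that condition backwards. The ready availability of a lower dose also does not help the tolerating child whose dose is reduced because the parenthesis was followed.

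The use of 9.35 is also open to challenge, since it concerns a cohort's starting dose and not an individual. That is fair. It shows only that the plan accepts high exposure once safety has passed.

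A reader might infer that the primary safety analysis would lose children. The documents do not support a shortfall. Section 3.3 replaces subjects who stop for reasons other than ETR toxicity, which plausibly covers a stop on AUC alone. Section 8.42 sets accrual (about 50) by what is needed to reach 36 evaluable, and Section 8.1 keeps all safety data in secondary analyses.

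**Conclusion.** Wrong as written; minor. The defect is certain from the text: the parenthesis in the second bullet of 9.34 contradicts the words it explains, and 6.8 omits the condition altogether. The literal rules would act on tolerating children at exposures that the cohort target accepts.

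The size is bounded only loosely. About 52% of children would exceed 4380 at the adult geometric mean, given log-normal AUC12h with adult spread. A reader might infer that half the children, or some definite number of the 36, would be stopped. Neither follows. The first ignores the second half of the 6.8 criterion. The second needs a rounding rule, a split of children across doses and a definition of when a dose cannot be reduced, none of which the documents give. The number stopped is zero on the plainest reading and otherwise undetermined, before any intervention by the protocol team. No sample size or analysis figure changes.

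**What to change.** 1. **Section 9.34, second bullet.** Change the parenthesis to *(toxicity ≥ Grade 3)*.
2. **Section 6.8, AUC bullet.** Replace with *AUC12h >4380 ng·h/mL with a dose that is not well tolerated and cannot be reduced, per Section 9.34*. Alternatively delete it: the first bullet of 6.8 already stops ETR for related Grade 3 or higher events, and 9.34 holds the rest of the rule.
3. **Settle the overlap.** State whether a child with a related Grade 3 or higher event and AUC12h above 4380 is to be dose reduced (9.34) or stopped (first bullet of 6.8). At present both apply.

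It is better not to add an at-least-possibly-related test to the AUC rule without thought. It would make the 6.8 AUC bullet redundant with the first bullet, and it would differ from the stricter probable-or-definite standard in the third bullet of 9.34. If a relatedness level is wanted, the sponsor should choose one deliberately.

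The cost is two wording corrections and one clarifying sentence in the protocol, with no change to visits, sample size or analysis.
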